9.8. Other Evaluations

Mid-turbinate nasal swabs collected at screening will be used to determine the presence of viral (other than RSV) or bacterial pathogens (both by multiplex PCR) at the central laboratory.

9.9. Sample Collection and Handling

The actual dates and times of sample collection must be recorded in the eCRF or laboratory requisition form.

Refer to the [TIME AND EVENTS SCHEDULE](#) for the timing and frequency of all sample collections.

Instructions for the collection, handling, storage, and shipment of samples are found in the laboratory manual that will be provided. Collection, handling, storage, and shipment of samples must be under the specified, and where applicable, controlled temperature conditions as indicated in the laboratory manual.

**10. SUBJECT COMPLETION/DISCONTINUATION OF STUDY TREATMENT/
WITHDRAWAL FROM THE STUDY****10.1. Completion**

A subject will be considered to have completed the treatment period of the study if he or she has completed dosing on the 7 days of the dosing period and the Day 8 visit. A subject is considered to have completed the study if he or she has also completed assessments of the last follow-up visit.

10.2. Discontinuation of Study Treatment/Withdrawal from the Study**Discontinuation of Study Treatment**

A subject will not be automatically withdrawn from the study if he or she has to discontinue treatment before the end of the treatment regimen.

A subject's study treatment must be discontinued if:

- The subject withdraws consent.
- The investigator believes that for safety reasons or tolerability reasons (eg, AE) it is in the best interest of the subject to discontinue study treatment.
- The subject becomes pregnant.

- The subject has a confirmed QTcF interval >500 ms at the Day 3 visit, per the machine read parameter result. Confirmation needs to be obtained during the visit by repeat triplicate ECG recording.
- The subject is reported with the following laboratory abnormalities: AST or ALT increases ≥ 3 x ULN at screening, confirmed in a repeat test, to be performed within 48 hours of the result being available at the site.
- The subject is reported with any other laboratory abnormality of grade 3 or 4, except for grade 3 or 4 elevations of triglycerides, low density lipoprotein cholesterol, and/or cholesterol at screening, confirmed in a repeat test, to be performed within 48 hours of the result being available at the site.

Subjects who prematurely discontinue study drug treatment for any reason (except withdrawal of consent) will be asked to continue with their remaining study visits and assessment schedule, or, at a minimum, to return to the site for a Withdrawal and a Safety Follow-up Visit. Subjects who withdraw consent during the treatment or follow-up phase will be offered and be encouraged to attend an optional Safety Follow-up Visit. At the Withdrawal and Safety Follow-up Visits, the same assessments as on the Day 8 and Day 21 visits, respectively, will be performed.

Withdrawal From the Study

A subject will be withdrawn from the study for any of the following reasons:

- Lost to follow-up.
- Withdrawal of consent.
- Death.
- The subject is poorly compliant with study procedures, study drug administration, visits, and assessments, after evaluation and discussion between the investigator and sponsor.
- Decision by the sponsor to stop or cancel the study.
- Decision by the investigator to withdraw subjects.
- Decision by local regulatory authorities and Independent Ethics Committee (IEC)/ Institutional Review Board (IRB) to stop or cancel the study.

Subjects who withdraw consent during the follow-up phase will be offered an optional Safety Follow-up Visit. At the Safety Follow-up Visits, the same assessments as on the Day 21 visits will be performed.

If a subject is lost to follow-up, every reasonable effort must be made by the study-site personnel to contact the subject and determine the reason for discontinuation/withdrawal. The measures taken to follow up must be documented.

When a subject withdraws before completing the study, the reason for withdrawal is to be documented in the eCRF and in the source document. Study drug assigned to the withdrawn subject may not be assigned to another subject.

10.3. Withdrawal From the Use of Research Samples

A subject who withdraws from the study will have the following options regarding the optional research samples:

- The collected samples will be retained and used in accordance with the subject's original separate informed consent for optional research samples.
- The subject may withdraw consent for exploratory biomarker research, in which case the samples will be destroyed and no further testing will take place. To initiate the sample destruction process, the investigator must notify the sponsor study site contact of withdrawal of consent for the optional research samples and to request sample destruction. The sponsor study site contact will, in turn, contact the biomarker representative to execute sample destruction. If requested, the investigator will receive written confirmation from the sponsor that the samples have been destroyed.

Withdrawal From the Use of Samples in Future Research

The subject may withdraw consent for use of samples for research (refer to Section 16.2.5). In such a case, samples will be destroyed after they are no longer needed for the clinical study. Details of the sample retention for research are presented in the main ICF.

11. STATISTICAL METHODS

Statistical analysis will be done by the sponsor or under the authority of the sponsor. A general description of the statistical methods to be used to analyze the efficacy and safety data is outlined below. Specific details will be provided in the Statistical Analysis Plan (SAP).

11.1. Interim Analysis

An interim analysis, encompassing efficacy, safety, and pharmacokinetics is planned after at least 36 subjects have been dosed and have completed the assessments of Day 8 as planned in the [TIME AND EVENTS SCHEDULE](#). Enrollment will not be paused during the interim analysis.

Investigators, subject(s) and local sponsor representatives will remain blinded. The central sponsor team members will be unblinded at time of the interim analysis.

Further details regarding the interim analysis will be specified in an interim SAP.

The central sponsor team members will review the unblinded interim efficacy, safety, and pharmacokinetic analyses and will make recommendations to the DRC regarding possible changes to the design of the study: dropping the lower dose, changing the stratification factor (and/or the requirement of maximum 50% of all enrolled subjects with symptom onset >3 days before randomization), changing the maximum number of days between RSV symptom onset and randomization and/or the number of time points/visits for collecting a nasal swab by HCP. The DRC will decide on the implementation of the recommendations based on the review of the results and other ongoing studies of JNJ-53718678 (see Section 11.9). The DRC will consist of senior sponsor personnel outside of the central sponsor team and not involved in study conduct.

Additional interim analyses may be performed at the sponsor's discretion to support decision making for further development of JNJ-53718678 and to support interactions with health authorities.

The primary (final) analysis will be performed after the last subject has completed his/her last visit of the study.

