3. STUDY DESIGN AND RATIONALE

3.1. Overview of Study Design

This is a Phase 2a, randomized, double-blind, placebo-controlled study to explore the antiviral activity, clinical outcomes, safety, tolerability, and pharmacokinetics of JNJ-53718678 at 2 dose levels (80 mg and 500 mg) once daily for 7 days in adult subjects with respiratory illness due to RSV infection. Subjects may be otherwise healthy or comorbid and should not be in need of hospitalization.

A population of 75 subjects is targeted. However, given the recruitment challenges associated with the seasonality of RSV, a minimum of 63 subjects may be considered sufficient to complete the study.

The study will include a Screening Period (Day -1 to Day 1), a Treatment Period (Day 1 to Day 8), and a Follow-up Period (Day 9 to Day 28[±3]). The total study duration for each subject will be 29 days (screening included).

Study participants will be identified when they present for medical care with symptoms supporting a diagnosis of RSV infection (eg, fever, cough, nasal congestion, runny nose, sore throat, myalgia, lethargy, shortness of breath, or wheezing). Screening should be completed as soon as possible; treatment initiation should start as soon as possible, but no later than 4 hours after randomization, which should occur within a maximum of 5 days after RSV symptom onset. During screening, mid-turbinate nasal swabs will be collected for local diagnosis of RSV infection (using a rapid polymerase chain reaction (PCR)-based or rapid-antigen-detection test), and for additional post-hoc analysis at a central laboratory to confirm RSV infection (and subtype), to determine the RSV viral load and the presence of other viral or bacterial pathogens.

After screening, eligible subjects will be randomized on Day 1 (1:1:1) to receive 1 of 3 treatments:

- Treatment A: 500 mg JNJ-53718678 once daily for 7 days (n = 25 [target]);
- Treatment B: 80 mg JNJ-53718678 once daily for 7 days (n = 25 [target]);
- Treatment C: placebo once daily for 7 days (n = 25 [target]).

In order to maintain study blind, all subjects will receive once daily the same total volume of study drug solution divided over 2 separate but sequential intakes at the same time of day (see Section 6 for more details).

Randomization will be stratified by time of symptom onset (≤ 3 days vs > 3 days before randomization). Subjects with symptom onset > 3 days before randomization may account for maximum of 50% of all enrolled subjects.

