9.2.3. Viral Sequencing

Viral resistance will be monitored by sequencing of the F-gene of the viral genome on all baseline samples and on post baseline samples upon request of the sponsor's protocol virologist. Other regions of the RSV genome may also be sequenced at the request of the protocol virologist. Sequencing data will not be reported to the investigators.

Changes in viral sequence will be evaluated but will not be reported as AEs.

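### Section 10.2 lets irregular dosing end a subject's viral-load follow-up, although subjects who stop study drug altogether are kept in follow-up

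*Protocol*

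**What the plan says.** Protocol Section 10.2 treats stopping study drug and leaving the study as separate matters. Stopping treatment does not by itself lead to withdrawal. Anyone who stops early without withdrawing consent is asked to complete the remaining schedule or, at the least, to attend a Withdrawal Visit (Day 8 assessments) and a Safety Follow-up Visit (Day 21 assessments).

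Under Withdrawal From the Study, the same section lists reasons for which a subject will be withdrawn. One is: "The subject is poorly compliant with study procedures, study drug administration, visits, and assessments, after evaluation and discussion between the investigator and sponsor".

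Section 11.4 defines the primary efficacy population as all randomized subjects with at least one dose and a centrally confirmed RSV infection. The primary virology in Section 2.1.2 includes AUC through Days 3, 5, 8 and 14, viral load over time, and time to undetectable. Under Section 9.2.1, swabs run daily to Day 8, continue daily to Day 13 at the latest while symptoms last, and are taken again on Days 14 and 21.

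On the interim, Section 11.1 says it is "planned after at least 36 subjects have been dosed and have completed the assessments of Day 8", that "Enrollment will not be paused during the interim analysis", and that "The central sponsor team members will be unblinded at time of the interim analysis". It adds: "Investigators, subject(s) and local sponsor representatives will remain blinded". Further interims are left to the sponsor's discretion. Section 5 restricts the release of codes to subjects included in the interim.

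**The concern.** An intent-to-treat type of population is meant to keep subjects in the comparison however well they took the drug. The compliance ground works against that. A subject who gives up the drug keeps contributing viral loads; a subject who takes it irregularly may be removed and contribute no more. Dosing behaviour arises after randomization and may depend on how the subject feels, on the course of the infection, or on the treatment itself. Missing values that arise this way need not be ignorable.

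At stake is the comparison of each dose with placebo on viral load, with about 24 analysable subjects per arm. Section 1.3 says the results will be used to select the dose and endpoints for later studies. A secondary question is whether sponsor staff who know the allocation of some subjects could take part in these withdrawal discussions, since Section 10.2 does not say which sponsor staff hold them.

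**Working it through.** **1. Is there a figure to reproduce?** No. Section 11.3 gives an overage of approximately 5% (72 to 75, a ratio of 75/72 = 1.042; 60 to 63 would be 1.05). It is justified by false-positive local tests and by stopping treatment for abnormal screening laboratory results. Withdrawal for poor compliance is not among the reasons, and no rate for it appears anywhere.

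**2. The rules side by side.**

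| Situation | Protocol section | Consequence for follow-up |
|---|---|---|
| A dose is missed by more than 12 hours | 7 | Dose skipped, next dose as scheduled; follow-up unaffected |
| Study drug stopped early, consent kept | 10.2, discontinuation | Asked to continue the schedule, or at least two further visits |
| Poor compliance with study drug, as judged by investigator and sponsor | 10.2, withdrawal | Withdrawn from the study; no threshold given |

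The last two rows overlap. A subject withdrawn for poor compliance during the dosing days has also stopped study drug early without withdrawing consent. One rule asks that subject to continue; the other takes the subject out.

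**3. What one withdrawal costs.** The window for AUC through Day 14 spans 14 − 1 = 13 days. If the last swab is on Day k, the unobserved share is (14 − k)/13:

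- k = 3: 11/13 = 85%; AUC through Day 3 is complete, the three longer AUCs are not.
- k = 5: 9/13 = 69%; AUCs through Days 3 and 5 are complete.
- k = 8: 6/13 = 46%; only AUC through Day 14 is incomplete.

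The values of k are illustrative. They show the loss for one subject, not an expected loss for the trial.

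**4. Effect on the analysis.** Section 11.4.1 specifies a restricted maximum likelihood repeated-measures model. It uses every visit that was observed, and its estimates are valid if missingness depends only on observed data. The later course of a withdrawn subject is then in effect inferred from subjects in the same arm who stayed. If poor compliers would have had different later viral loads, for instance because they took less drug, the active-arm mean shifts towards that of subjects who dosed as planned. That direction assumes an active drug. The amount depends on how many are withdrawn and when, and the protocol gives neither.

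**5. Overlap with the interim unblinding.** The fractions are 36/75 = 48.0% of the target ("A population of 75 subjects is targeted") and 36/63 = 57.1% of the minimum ("a minimum of 63 subjects may be considered sufficient to complete the study"). Both are lower bounds, because the trigger is at least 36. Subjects who meet the trigger have reached the end of the seven-dose regimen and have their AUC through Day 8 collected. A decision made with knowledge of their arm could touch only what follows: 6 of 13 days (46%) of the Day 14 window, and the Day 14 and Day 21 swabs where these are outstanding. The protocol does not say whether subjects short of Day 8 may be included in the interim, and it sets no limit on further interims.

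**The case against.** The strongest reply is that little is at risk. This is a pilot Phase 2a study without formal testing. Swabs already collected stay in the model. The bullet covers procedures, visits and assessments as well as drug intake, and a subject who does not attend yields no data whatever the rule says. The investigator, who shares the decision, stays blinded. All of this stands and limits the size of the problem. It does not resolve the conflict between the two rules for a subject who attends and is swabbed but doses irregularly.

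A reader might go further in five ways, none of which the protocol supports:

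- **That the unblinded team will steer withdrawals by arm.** Codes go out only for interim subjects, and those who meet the trigger have no scheduled doses left on which to be non-compliant. Viral load is a central-laboratory qRT-PCR result. Nothing says that the central team, rather than blinded local representatives, holds the compliance discussion.
- **That each withdrawal removes 1/24 = 4.2% of an arm's primary data, so that two or three remove 8% to 12%.** This counts the whole subject as lost, but earlier swabs are kept, and the counts have no source in the protocol.
- **That taste or gastrointestinal effects will make non-compliance differ by arm.** Section 1.1 reports dysgeusia in 10.8% on drug against 0.0% on placebo in earlier studies, but says a study was started to optimise the taste. It attributes the diarrhea imbalance mostly to a study without placebo. Under Section 14.1 the placebo is the same vehicle. A difference is possible, not shown.
- **That the choice of samples for sequencing is compromised.** Post-baseline sequencing is done "on post baseline samples upon request of the sponsor's protocol virologist", but it is exploratory, and nothing says that person is unblinded.
- **That interim results must be confined to the Data Review Committee.** The sponsor-team review is openly declared, and a committee outside study conduct decides on changes. This is a debatable design choice, not an error. When the analysis rules are locked may be settled in plans not shown here.

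**Conclusion.** The point holds as a conflict within Section 10.2, and between that section and the primary population in Section 11.4. Poor compliance with study drug can end viral-load collection, while stopping the drug does not. The missing data this creates are potentially informative. Whether they would be depends on how non-compliance relates to treatment and to later viral load, which the protocol cannot show. The size of any bias cannot be computed without a withdrawal rate; for a single subject the unobserved part of the Day 14 window is 46% to 85% in the illustrations above. The gap over unblinded staff is secondary. It concerns mainly data after Day 8 in interim subjects, and it widens only if subjects short of Day 8 are included or further interims are run.

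**What to change.** Reconcile the passages in Section 10.2. In the withdrawal list, delete poor compliance with study drug administration as a ground for leaving the study, and state that such subjects keep their swabs and visits as other treatment discontinuers do. The remainder of the bullet can stay. This changes follow-up only, not any dosing or treatment-stopping rule.

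As a safeguard, add one sentence to Section 10.2 or 11.1: once any interim has been unblinded, the sponsor's part in discussions about withdrawing individual subjects is taken by staff who remain blinded.

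The cost is an edited bullet, one added sentence and some further follow-up of poorly compliant subjects. The sample size does not change.

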11.2. Subject Information

For all subjects who receive at least 1 dose of study drug descriptive statistics will be provided.

All demographic (eg, age, length, weight, race, gender) and other initial subject characteristics (physical examination, medical and surgical history, family history, concomitant diseases) will be tabulated and analyzed descriptively by treatment group.

11.3. Sample Size Determination

The interim results (estimates of mean AUC and change from baseline of RSV viral load \pm SD) of study 53718678RSV1005 were the basis of the sample size calculation. In that study, median (range) time to onset of symptoms was 5 (2-12) days and baseline viral load was 5.3 (2.1-8.3) \log_{10} copies/mL.

For the AUC viral load from Day 1 to Day 7, a (placebo) point estimate of 490 and an SD of 135 \log_{10} copies x hr/mL was observed for the AUC viral load from Day 1 to Day 7. The sample size was determined in order to obtain estimates of the mean AUC viral load with a precision of approximately 50 \log_{10} copies x hr/mL of the true value with 90% confidence; with 20 subjects per treatment group the half-width of the 90% confidence would be approximately 52 and with 24 subjects per treatment group the precision would be approximately 47 \log_{10} copies x hr/mL.

For the change from baseline (on Day 2 or Day 3), (placebo) point estimates of -0.11 and -0.33 and SDs of 1.85 and 1.56 \log_{10} copies/mL, respectively, were observed. The observed difference (active versus placebo) was -1 to -2 \log_{10} copies/mL. With an assumed SD of 1.85 \log_{10} copies/mL, 20 subjects per treatment group will lead to a precision (90% confidence interval [CI] half width) of 0.986 and 24 subjects per treatment group to a precision of 0.896 \log_{10} copies/mL for the estimate of the difference between active dose and placebo .

As further guidance for the design, the power to detect a dose-response was calculated. To evaluate a potential dose-response, 3 contrasts will be tested: a contrast with no difference between the 2 active doses tested against placebo; a contrast with no difference between low dose and placebo tested against high dose; and a contrast with a linear dose-response relationship with respect to the active doses. No correction for multiplicity is considered in view of the exploratory nature of the study. Based on 10,000 simulations, and assuming a reduction in AUC viral load of 20% of high dose versus placebo, the power to detect a positive dose-response relationship will be between 79% and 86% (depending on the effect of the low dose) with a total sample size of 60, and between 83% and 89% with a total sample size of 72.

To account for potential false-positive RSV screening testing (ie, diagnosed with RSV infection using a rapid PCR-based or rapid antigen-detection test, but negative at the central lab using a qRT-PCR assay, and therefore not included in the primary analysis population of ITT-i) and withdrawals from treatment for abnormal screening laboratory results, an overage of approximately 5% will be enrolled, ie, 75 subjects will be targeted.

In view of the seasonality of the disease, recruitment will be halted if at the end of an hemispheric RSV season 63 or more subjects have been enrolled and dosed. If at the end of an hemispheric RSV season the minimum of 63 dosed subjects is not reached, recruitment will continue in a next RSV season until this minimum has been reached, up to a maximum of 75 subjects to be enrolled overall.

11.4. Efficacy Analyses

The primary population for the efficacy/antiviral activity analysis will be the intent-to-treat infected population consisting of all randomized subjects who received at least one dose of study treatment and who have a central lab-confirmed RSV infection.

11.4.1. Antiviral Effect

To explore the antiviral effect on RSV, as measured by qRT-PCR assay in mid-turbinate nasal swabs, the following virologic parameters will be assessed:

- AUC from immediately prior to first dose of study drug (baseline) through Day 3, Day 5, Day 8, and Day 14
- RSV viral load and change from baseline over time
- Time to undetectable RSV viral load
- Proportion of subjects with undetectable RSV viral load at each time point throughout the study

If feasible, the RSV infectious virus titers as measured by quantitative culture of RSV (plaque assay) on selected nasal swab samples, may also be assessed.

Endpoints will be analyzed graphically and descriptively as described in the SAP. For continuous variables descriptive statistics (n, mean, SD, median, minimum, and maximum) will be calculated. For viral efficacy parameters also 90% CIs will be computed comparing active dose groups versus placebo. For categorical variables, frequency tables will be presented. Kaplan-Meier Curves will be produced to graphically describe the time to event data.

To explore the antiviral effect, \log_{10} viral load values over time will be analyzed using a restricted maximum likelihood-based repeated measures approach. Analyses will include the fixed, categorical effects of treatment, strata, visit, and treatment-by-visit interaction, as well as the continuous, fixed covariates of baseline \log_{10} viral load and baseline \log_{10} viral load by-visit interaction. An unstructured (co)variance structure will be used to model the within-subject errors over time. The differences in the AUCs for active versus placebo will be derived using

appropriate contrasts deriving least squares mean differences, including the 90% 2-sided CIs. Details will be provided in the SAP.

Additional analyses will be performed to investigate other endpoints, including exploratory endpoints. Details on these analyses will be provided in the SAP.

